Detachable string magnetically controlled capsule endoscopy for completely viewing the esophagus and stomach: study protocol for a self-controlled single-center study

Document Date: March 1, 2018

Trial registration: ClinicalTrials.gov ID: NCT03457909

Objective

Esophageal capsule endoscopy (ECE) was reported not accurate enough to replace EGD as the passive passage of ECE through the esophagus precluded a thorough investigation. We developed a modified capsule endoscopy, called detachable string magnetically controlled capsule endoscopy (DS-MCE) and performed a pilot study to assess the feasibility and safety of DS-MCE.

Study design

This study is a prospective, single-centered pilot study. The study protocol has been approved by the institutional review board of Shanghai Hospital (Second Military Medical University, Shanghai, China).

Study patients

Healthy volunteers and patients with suspected esophageal diseases will be prospectively enrolled in Shanghai Hospital from March 2018 to June 2018. Patients with any MCE contradictions will be excluded.

Study intervention

After enrollment, each subject will first undergo DS-MCE, and subsequently EGD within one week. DS-MCE will be performed by an endoscopist ([name]) with an experience of >500 cases of MCE operation. Another endoscopist ([name]) who is blinded to the DS-MCE diagnosis will perform the EGD examinations and interpret the images. EGD examination are carried out under topical pharyngeal anesthesia induced by a

single oral dose of 100 mg dyclonine hydrochloride.

Capsule endoscopy devices and procedure

Procedures are performed using the NaviCam magnetic capsule guidance system (Ankon Technologies, Shanghai, China). The DS-MCE system consists of two parts, a thin and transparent latex sleeve with an 80cm long hollow string attached to its cauda end and a sterile syringe for single use. The capsule partially enclosed in the sleeve can be detached from the string system through injecting air into the hollow string with the syringe. In a left lateral position, subjects swallow the capsule with water, without any sedation. The capsule is allowed to travel down approximating the gastric cardia, from where the string is slowly pulled up to inspect the esophagus under the guidance of real-time viewing. Images are captured at a rate of 2 frames per second. Target areas of interest can be observed repeatedly. If bubbles obscure the view, subjects are instructed to sip a little water until the esophageal image improved. After completing the esophagus examination, the string is separated from the capsule through injecting 5 ml air with the syringe, taken out of the mouth and discarded, while the capsule entered the stomach with additional water ingestion. Stomach examination and small bowel examination (if needed) are carried out according to standardized protocol.

Study outcomes

Primary outcome is the success rate of DS-MCE, a composite outcome defined as the success rate of completely viewing the esophagus (from the capsule being swallowed, the esophagus observed retrograde, to the string being pulled out after separating from the capsule), detachment of string and capsule at the end of esophageal examination and entering the stomach. Secondary outcomes include safety, discomfort associated with the procedure, diagnostic accuracy, image quality and Z-line visualization. All patients will be followed up to 2 weeks to confirm capsule excretion and any adverse events. Any discomfort during the procedure is evaluated with the Ramirez system and our previous system, on a scale from 0 to 3 (0, no; 1, mild/minimal; 2,

moderate; and 3, severe/very difficult). Overall discomfort is scored on a scale of 0 to 10 (0, no discomfort; 10, the overall discomfort of EGD). Also, subjects will be asked the preference of DS-MCE and EGD. The diagnostic accuracy of DS-MCE is assessed by esophageal diagnosis and grade of reflux esophagitis and esophageal varices in comparison to EGD. Reflux esophagitis and esophageal varices identified during EGD and DS-MCE are classified using the Los Angeles classification, Baveno III consensus and DFC.

All the images obtained by DS-MCE are monitored in real time and capsule findings were documented by an experienced endoscopist ([name]). Another endoscopist ([name]) independently graded Z-line viewing (the number of quadrants captured on the Z-line), image quality and the air bubbles with our previous system. The bubble grade ranges from 0 to 3 (0, no bubble; 1, a few bubbles; 2, increased amount of bubbles; 3, severe bubbles). Image quality grade ranges from 1 to 10 (1, the worst quality; 10, the quality of the image captured by EGD).

Central contact

[name]

National Clinical Research Center for Digestive Diseases; Department of Gastroenterology, Changhai Hospital, Second Military Medical University, [name]

[contact]; [contact]

E-mail: [contact]

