Statistical analysis Plan

Document Date: March 1, 2018

Trial registration: ClinicalTrials.gov ID: NCT03457909

Study outcomes

Primary outcome is the success rate of DS-MCE. Secondary outcomes include safety, discomfort associated with the procedure, diagnostic accuracy, image quality and Z-line visualization. All patients will be followed up to 2 weeks to confirm capsule excretion and any adverse events. Any discomfort during the procedure is evaluated with the Ramirez system and our previous system, on a scale from 0 to 3 (0, no; 1, mild/minimal; 2, moderate; and 3, severe/very difficult). Overall discomfort is scored on a scale of 0 to 10 (0, no discomfort; 10, the overall discomfort of EGD). Also, subjects will be asked the preference of DS-MCE and EGD. The diagnostic accuracy of DS-MCE is assessed by esophageal diagnosis and grade of reflux esophagitis and esophageal varices in comparison to EGD. Reflux esophagitis and esophageal varices identified during EGD and DS-MCE are classified using the Los Angeles classification, Baveno III consensus and DFC.

The bubble grade ranges from 0 to 3 (0, no bubble; 1, a few bubbles; 2, increased amount of bubbles; 3, severe bubbles). Image quality grade ranges from 1 to 10 (1, the worst quality; 10, the quality of the image captured by EGD).

Statistical analysis

Quantitative data (age, comfort assessment, image quality) are summarized with the mean (range) and the median (range), while categorical data (sex, success rate of DS-MCE) are presented as frequency (percentage). The diagnostic accuracy is analyzed by fourfold table.

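### Every subject has both DS-MCE and EGD, but for discomfort and preference the SAP plans no paired estimate and no confidence interval

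*Protocol*

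**What the plan says.** The protocol title describes a "study protocol for a self-controlled single-center study". Under Study intervention, "each subject will first undergo DS-MCE, and subsequently EGD within one week", so each subject can serve as their own control. The Objective is narrower than a comparison of two procedures: the investigators "performed a pilot study to assess the feasibility and safety of DS-MCE".

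Discomfort is a secondary outcome in both documents. Under Study outcomes the protocol states: "Any discomfort during the procedure is evaluated with" two existing scoring systems, graded 0 to 3. It does not say that EGD is graded on the same items. A separate overall score runs from 0 to 10, with 10 defined as the discomfort of EGD as a whole. Subjects are also asked which procedure they prefer.

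The SAP's Statistical analysis section covers comfort in one sentence: "Quantitative data (age, comfort assessment, image quality) are summarized with the mean (range) and the median (range". Categorical data are given as counts and percentages, with sex and DS-MCE success as the named examples. Preference is not mentioned in that section, and no confidence interval is planned for any outcome. For diagnosis the SAP does compare the two procedures: "The diagnostic accuracy of DS-MCE is assessed by esophageal diagnosis and grade of reflux esophagitis and esophageal varices in comparison to EGD", analyzed by a fourfold table.

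**The concern.** A trial that measures discomfort and asks which of two procedures the subject prefers will be read as evidence on relative tolerability, whatever its stated objective. Each subject undergoes both procedures, so the natural quantity is the within-subject difference, with a measure of its uncertainty. The plan specifies neither for the 0-3 items. If EGD is not scored on them, no difference exists to analyze. If it is, two separate summaries with ranges do not show how many subjects found DS-MCE easier, the same or harder, nor how precisely the difference is known.

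At stake is what the pilot can say about tolerability and how well it can inform a later study. The primary outcome is not affected.

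**Working it through.** **Inputs.** Neither document gives a sample size, standard deviation, correlation or expected preference rate, so there is no figure of the plan's own to reproduce. Values marked as assumed below are illustrations.

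**1. Which outcomes already use the pairing?**

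| Outcome | Planned analysis | Within-subject use of EGD | Interval |
|---|---|---|---|
| DS-MCE success (primary) | Count, percentage | None; EGD has no counterpart | None |
| Diagnosis and grade | Fourfold table against EGD | Yes | None named |
| 0-3 discomfort items | Mean and median with ranges | EGD scoring not stated | None |
| 0-10 overall discomfort | Mean and median with ranges | Through the anchor only | None |
| Preference | None named | Yes, by the question itself | None |

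The fourfold table does keep the pairing. Take an assumed table of 20 subjects: 9 positive on both, 1 on DS-MCE only, 1 on EGD only, 9 negative on both. Sensitivity is 9/(9+1) = 0.90 (exact 95% CI 0.555 to 0.997), and the paired difference in positive rates is (1-1)/20 = 0. The gap is therefore confined to discomfort and preference.

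**2. Can the 0-10 score stand in for a paired difference?** With EGD fixed at 10, the implied difference for a subject is 10 minus the score. Scores lie between 0 and 10, so this runs from 10-10 = 0 to 10-0 = 10 and is never negative. A subject who found DS-MCE worse than EGD must record 10, the same as one who found them equal. The mean implied difference exceeds 0 unless every subject scores 10. The time of scoring is not stated either. A score taken straight after DS-MCE would precede the study EGD that defines its anchor.

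**3. What do separate summaries lose?** With complete pairs, the difference between the two means equals the mean of the within-subject differences, so that point estimate survives. Its uncertainty does not. The variance of a difference is s1² + s2² - 2·rho·s1·s2, and rho cannot be recovered from two means, medians and ranges. Nor can the better/same/worse counts.

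**4. How much does pairing help?** With equal variances, the variance of the paired mean difference is 2s²(1-rho)/n, against 2s²/n if the scores are treated as unpaired. The ratio of standard errors is sqrt(1-rho):

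- rho = 0.3 (assumed): sqrt(0.7) = 0.837, about 16% smaller.
- rho = 0.6 (assumed): sqrt(0.4) = 0.632, about 37% smaller.

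**5. How imprecise might preference be?** For an assumed 20 of 25 preferring DS-MCE, the proportion is 20/25 = 0.80. The Clopper-Pearson limits are the 2.5% point of Beta(20, 6) and the 97.5% point of Beta(21, 5), which are 0.593 and 0.932. A bare 80% would hide a lower limit near 59%.

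**The case against.** The strongest reply is that this is a descriptive pilot. Its objective is feasibility and safety, and its primary outcome is a DS-MCE success rate. EGD is there chiefly as the diagnostic reference, read by an endoscopist "who is blinded to the DS-MCE diagnosis will perform the EGD examinations and interpret the images". On that view the second examination earns its place without any discomfort comparison, and the 0-10 score and the preference question are already relative to EGD.

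Much of this stands. A reader might infer from the title that the design exists to contrast the two procedures and that the SAP never estimates that contrast. The documents do not support either reading: the objective does not state such a contrast, and the fourfold table is a within-subject comparison. Nor is the second procedure wasted.

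Three further points stand. The SAP plans no unpaired test or interval, so the 16% to 37% figure is not a loss that this plan incurs. The content of the two scoring systems is not reproduced, so some 0-3 items may have no meaning for EGD. DS-MCE always comes first, and EGD is done under topical throat anesthesia whereas DS-MCE is done without sedation, so even a good paired estimate mixes procedure with order and preparation.

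The reply does not dispose of the capped overall scale, the silence on scoring EGD with the 0-3 items, or the absence of an analysis and interval for preference.

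**Conclusion.** The point holds for discomfort and preference only. Every subject has both procedures, yet the SAP plans no paired estimate on the 0-3 items and no interval for any tolerability result, and the one EGD-anchored score cannot show DS-MCE to be worse. This is under-specification of secondary outcomes in a pilot. It does not touch the primary outcome and is not an absence of all within-subject comparison.

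Its size cannot be fixed from the documents. The 16% to 37% reduction in standard error rests on equal variances and an assumed correlation of 0.3 to 0.6. The 59% to 93% interval rests on an assumed 20 of 25. Both only illustrate what pairing and an interval would add. The change should be made because it is cheap and decides what the trial can say about tolerability.

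**What to change.** 1. In the protocol's Study outcomes, list the 0-3 discomfort items that apply to both procedures, and give them right after DS-MCE and again right after EGD. State when the 0-10 score and the preference question are asked.
2. In the SAP, for each shared item, report the number of subjects for whom DS-MCE was better, the same or worse than EGD, and the within-subject difference with a 95% CI, for example the Hodges-Lehmann estimate with its Wilcoxon signed-rank interval. Note that differences on a four-level item take only whole values from -3 to 3, so ties will be many and the interval coarse; the counts should lead.
3. Report the proportion preferring DS-MCE with an exact 95% CI, and say how a subject with no preference is counted.
4. Say that the 0-10 score is bounded at EGD and cannot show DS-MCE to be worse, and that the fixed order and the topical anesthesia used for EGD limit interpretation of any difference.

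The cost is one repeat of a short questionnaire and a few lines of analysis text. No extra procedure or staff is needed, and the examinations do not change.

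### The overall-discomfort score is capped at the discomfort of EGD, so a mean below 10 does not by itself show that DS-MCE is less uncomfortable.

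*Protocol*

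**What the plan says.** Discomfort is a named secondary outcome in the protocol (Study outcomes): "Secondary outcomes include safety, discomfort associated with the procedure, diagnostic accuracy, image quality and Z-line visualization". Its overall rating is defined there, and identically in the SAP: "Overall discomfort is scored on a scale of 0 to 10 (0, no discomfort; 10, the overall discomfort of EGD". No value is provided for a procedure worse than EGD.

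The SAP (Statistical analysis) plans only this for the score: "Quantitative data (age, comfort assessment, image quality) are summarized with the mean (range) and the median (range". It plans no count of subjects at 10, no confidence interval and no comparison with EGD.

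Three other statements matter:

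- **Design.** The protocol's title calls it a "study protocol for a self-controlled single-center study", and Study design says: "This study is a prospective, single-centered pilot study".
- **Order.** Under Study intervention, "each subject will first undergo DS-MCE, and subsequently EGD within one week". Neither document says when the 0–10 score is collected.
- **Other measures.** Discomfort is also graded by the Ramirez system and "our previous system, on a scale from 0 to 3", and "subjects will be asked the preference of DS-MCE and EGD". The documents do not say whether the 0–3 items are also completed for EGD, and they give no analysis for preference.

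**The concern.** A scale whose maximum is the comparator can record that DS-MCE is milder than EGD but not that it is worse. Subjects who find DS-MCE milder lower the mean by the full amount of their difference. Subjects who find it worse cannot offset them, because they are recorded as equal. The mean can therefore sit clearly below the EGD value when the procedures are equally unpleasant on average, or even when DS-MCE is the more unpleasant.

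In a self-controlled study, a score topped at EGD invites comparison with EGD. A reader who takes a mean below 10 as less discomfort than EGD would be relying on a result that the scale produces almost automatically.

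Timing adds a smaller uncertainty. If the score is taken after DS-MCE but before EGD, the upper anchor is not the EGD that the subject has in this study.

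**Working it through.** **Inputs.** The documents supply the closed 0–10 range, the anchor at 10 and the planned summaries. They give no sample size, SD, expected score or correlation, so there is no stated figure to reproduce. Steps 1 and 2 need no distribution. Every mean, SD, correlation and sample size in steps 3 to 5 is an assumption.

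**1. Bounds.** Every score is at most 10, so the mean is 10 only if all subjects score 10. If a share p scores 10 and the rest score at least 0, then mean ≥ 10p, so p ≤ mean/10.
- Mean 8.5: up to 85% may be at the cap. This is the extreme case, in which the other 15% all score 0.
- Mean below 5: fewer than half are at the cap, so more than half scored under the anchor.

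**2. Ten-subject example.** On an absolute scale, six subjects rate DS-MCE 8 and EGD 5; four rate DS-MCE 3 and EGD 6.
- True mean difference (DS-MCE minus EGD): (6×3 − 4×3)/10 = +0.6, so DS-MCE is worse.
- If subjects answer by ratio, 10 × min(DS-MCE/EGD, 1): (6×10 + 4×5)/10 = 8.0.
- If subjects answer by difference, 10 − max(EGD − DS-MCE, 0): (6×10 + 4×7)/10 = 8.8.
- The median is 10 either way.

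**3. Relative discomfort assumed normal, EGD = 10, recorded score cut to 0–10.** Ignoring the lower limit, with true mean 10 + δ, SD σ and d = δ/σ, the recorded mean is 10 − σ[φ(d) − d(1 − Φ(d))]. With δ = 0 this is 10 − 0.399σ. Simulated values:

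| True mean | SD 1 | SD 2 | SD 3 | SD 4 |
|---|---|---|---|---|
| 10 (no difference) | 9.60 | 9.20 | 8.80 | 8.41 |
| 12 (DS-MCE worse) | 9.99 | 9.83 | 9.55 | 9.21 |

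The median is 10 in every cell.

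**4. Paired absolute ratings.** Simulated with bivariate normal discomfort clipped to 0.1–10, SD 1 to 3 and correlation 0 to 0.7, and scored by the two rules of step 2 without rounding:

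| True means, DS-MCE vs EGD | Mean score, ratio | Mean score, difference | Share at 10 |
|---|---|---|---|
| 5 vs 5 | 7.61–9.42 | 8.43–9.69 | 49.9–51.9% |
| 5.5 vs 4.5 | 8.18–9.93 | 8.84–9.96 | 59.5–90.2% |
| 2 vs 7 | 2.79–3.81 | 5.01–5.70 | 0–12.2% |

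The population median is 10 in the first two rows. With DS-MCE milder by one point (4.5 vs 5.5) it falls to 8.2–8.4 (ratio) or 9.0–9.2 (difference). Whole-number answers raise the share at 10 to 52.7–74.0% under equal truth, and to at most 14.8% at 2 vs 7.

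**5. Samples of 20 to 60 (assumed).**
- Equal truth: the mean is below 10 in at least 99.7% of samples and below 5 in at most 0.04%. A range maximum below 10 did not occur.
- DS-MCE worse by 1 (5.5 vs 4.5): the mean is still below 10 in 41–100% of samples, depending on the assumptions.
- A larger gap (6 vs 4) with SD 1 and whole-number answers: this can drop to about 1% at n = 20.
- Sample median under equal truth: below 10 in 43–59% of samples (unrounded) or 0–49% (whole numbers). This is ordinary sampling error, not bias from the cap.

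**The case against.** The strongest reply is that the plan never proposes the inference being criticised. The SAP is descriptive, sets no test against 10 and has no rule for declaring DS-MCE milder; the stated aim is feasibility and safety. That is true, and it limits the weight of the point. It does not remove the point, because a score topped at EGD will be read against EGD.

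Second, the planned median largely separates the cases at population level, and the preference question can go against the device. Both hold. But the median in a small sample is noisy, preference is not a discomfort rating, and a reported range reaching 10 does not show whether one subject or most were at the cap.

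Third, a mean close to 10 is itself unfavourable to DS-MCE, so the score is not blind to a poor result. This stands: the accurate statement is that the mean cannot exceed the EGD value, not that it can show only benefit. Any single score below 10 also does mean that this subject rated DS-MCE milder.

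Fourth, the magnitudes depend on assumed distributions, and the 85% bound is extreme. Both are so; the core claim needs neither.

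Fifth, the missing confidence interval and the unstated timing are separate matters. An interval around a capped mean would not repair the cap, and scoring after both procedures is a natural reading. These are reporting gaps that can be closed in the same edit.

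**Conclusion.** The concern holds at minor severity. The cap follows from the wording of both documents and needs no assumption: results worse than EGD cannot be recorded, their size cannot be recovered, and a mean below 10 alone is not evidence of less discomfort.

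The practical size depends on the truth. If the procedures are about equally unpleasant, roughly half of subjects or more sit at the cap and the mean is about 7.6 to 9.7. If DS-MCE is much milder (2 vs 7), at most 15% do, and the distortion is small. These ranges rest on the assumed SDs, correlations and answering rules above.

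A mean below 5, a median below 10 or a range maximum below 10 remains informative about the subjects studied. The 0–3 items, the preference question, the primary outcome and diagnostic accuracy are not affected.

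**What to change.** **Preferred.** Ask each subject to rate overall discomfort on the same absolute 0–10 scale (0 = none, 10 = worst imaginable) immediately after DS-MCE and again immediately after EGD. Report the within-subject difference with a 95% CI, as description. The fixed order of procedures remains a limitation.

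**Minimum, if the EGD-anchored score is kept.** State that it is collected after EGD. Report the number and proportion scoring 10, with a 95% CI, beside the mean and median. Say in the SAP that a mean below 10 alone will not be read as less discomfort than EGD. This covers much of the problem without the absolute scale, although it still cannot separate equal from worse.

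**Cost.** One added question if the absolute scale replaces the anchored score, two if both are kept, plus small edits to the case report form and SAP. No extra procedure, visit or staff is needed.

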Statistical analysis Plan

Document Date: March 1, 2018

Trial registration: ClinicalTrials.gov ID: NCT03457909

Study outcomes

Primary outcome is the success rate of DS-MCE. Secondary outcomes include safety, discomfort associated with the procedure, diagnostic accuracy, image quality and Z-line visualization. All patients will be followed up to 2 weeks to confirm capsule excretion and any adverse events. Any discomfort during the procedure is evaluated with the Ramirez system and our previous system, on a scale from 0 to 3 (0, no; 1, mild/minimal; 2, moderate; and 3, severe/very difficult). Overall discomfort is scored on a scale of 0 to 10 (0, no discomfort; 10, the overall discomfort of EGD). Also, subjects will be asked the preference of DS-MCE and EGD. The diagnostic accuracy of DS-MCE is assessed by esophageal diagnosis and grade of reflux esophagitis and esophageal varices in comparison to EGD. Reflux esophagitis and esophageal varices identified during EGD and DS-MCE are classified using the Los Angeles classification, Baveno III consensus and DFC.

The bubble grade ranges from 0 to 3 (0, no bubble; 1, a few bubbles; 2, increased amount of bubbles; 3, severe bubbles). Image quality grade ranges from 1 to 10 (1, the worst quality; 10, the quality of the image captured by EGD).

Statistical analysis

Quantitative data (age, comfort assessment, image quality) are summarized with the mean (range) and the median (range), while categorical data (sex, success rate of DS-MCE) are presented as frequency (percentage). The diagnostic accuracy is analyzed by fourfold table.

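### No confidence interval is planned for the primary success rate or the accuracy table, so a bare percentage is the only planned primary result

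*SAP*

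**What the plan says.** The SAP's Statistical analysis section is two sentences long.

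- **Primary outcome:** "categorical data (sex, success rate of DS-MCE) are presented as frequency (percentage". The success rate is thus treated like a baseline characteristic.
- **Accuracy:** "The diagnostic accuracy is analyzed by fourfold table". No measure (sensitivity, specificity, overall agreement), unit of analysis or interval is named.
- **Adverse events:** SAP, Study outcomes, says "All patients will be followed up to 2 weeks to confirm capsule excretion and any adverse events". The Statistical analysis section does not name adverse events among the categorical data, so their summary is unspecified.

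Protocol, Objective, gives the purpose: the investigators "performed a pilot study to assess the feasibility and safety of DS-MCE". Protocol, Study patients, gives a population and a recruitment window but no number: "Healthy volunteers and patients with suspected esophageal diseases will be prospectively enrolled in Shanghai Hospital from March 2018 to June 2018". Neither document mentions a standard error, confidence interval, significance level, hypothesis test, performance goal or sample size. Nothing suggests that such text was redacted.

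**The concern.** A descriptive pilot needs no hypothesis test. Without one, though, the estimate is the whole result, and an interval is the natural way to say how much weight it bears. With no stated sample size, the plan gives no advance indication of precision either.

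The conclusions at stake are the two that the protocol sets out to reach. If all procedures succeed, feasibility would be reported as 100%; if no adverse event occurs, safety would be reported as none seen. Both are plausible results in a small series, and both look more certain than they are when no interval is attached. Accuracy has the same gap on what may be a smaller base, because the study mixes healthy volunteers with patients and only EGD-positive subjects contribute to sensitivity.

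**Working it through.** **Inputs.** The plan gives no figure to reproduce: no sample size, expected rate, target or error level. Every n below, and every split by EGD result, is assumed and serves only to show the range.

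**Formula.** Two-sided 95% Clopper-Pearson limits for x successes in n: lower = Beta(0.025; x, n−x+1), upper = Beta(0.975; x+1, n−x), both beta quantiles. If x = n, the lower limit is 0.025^(1/n) and the upper is 100%. If x = 0, the lower limit is 0 and the upper is 1 − 0.025^(1/n).

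**Primary success rate.** For 20/20: 0.025^(1/20) = 0.832.

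| Assumed n | All succeed | One failure |
|---|---|---|
| 20 | 83.2% to 100% | 19/20 = 95.0% (75.1% to 99.9%) |
| 30 | 88.4% to 100% | 29/30 = 96.7% (82.8% to 99.9%) |
| 50 | 92.9% to 100% | 49/50 = 98.0% (89.4% to 99.9%) |

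The same reported 100% therefore carries a lower limit that differs by 92.9 − 83.2 = 9.7 points between 20 and 50 subjects. Wilson limits are close: 83.9% for 20/20 and 92.9% for 50/50.

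**No adverse events.** For 0/20: 1 − 0.832 = 0.168. The upper limits are 16.8% (0/20), 11.6% (0/30) and 7.1% (0/50).

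**Accuracy**, assuming 30 subjects with both examinations, 5 EGD-positive and 25 EGD-negative:
- Sensitivity: 5/5 gives 47.8% to 100%; 4/5 = 80.0% gives 28.4% to 99.5%.
- Specificity: 25/25 gives 86.3% to 100%; 24/25 = 96.0% gives 79.6% to 99.9%.

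**Is sensitivity always the less precise figure?** No. Assume 20 subjects of whom 15 are EGD-positive. Sensitivity of 15/15 has limits 78.2% to 100%, a width of 21.8 points. A success rate of 18/20 has limits 68.3% to 98.8%, a width of 30.5 points. Lower precision is likely if few subjects are EGD-positive, but it is not guaranteed.

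**Separate minor check, the primary denominator.** Assume that 2 of 30 subjects cannot swallow the capsule and the other 28 succeed. Counting all attempts gives 28/30 = 93.3% (77.9% to 99.2%). Leaving out the two gives 28/28 = 100% (87.7% to 100%). This moves the estimate itself, so it differs in kind from the missing interval.

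**The case against.** The strongest reply is that little is lost. Counts will be reported with the percentage, so any reader can compute the interval for the primary outcome. No decision rule depends on precision. The real limit is the unstated sample size, which an interval does not mend. The figures above show general binomial behaviour at assumed numbers, not an effect measured in this trial. All of this stands, and it keeps the point small. It answers less well for accuracy: since the SAP names no measure and no unit, what a reader could reconstruct depends on choices made later.

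Four stronger readings are tempting, and the documents do not support them.

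- *The results would be invalid.* A percentage without an interval is still a correct estimate; only its interpretation suffers.
- *Sensitivity must be less precise than the success rate.* Interval width depends on the observed proportion as well as the number, and the number of EGD-positive subjects is not given.
- *Adverse events are planned as a bare percentage.* The SAP does not list them under that rule; it leaves their summary open.
- *Failed swallows will be dropped.* Nothing says so. Protocol, Study intervention, points to everyone: "After enrollment, each subject will first undergo DS-MCE, and subsequently EGD within one week". The outcome is "a composite outcome defined as the success rate of completely viewing the esophagus (from the capsule being swallowed", and its reference to swallowing may mean either a required step or merely the start of the observed interval. The text neither excludes such subjects nor expressly counts them as failures.

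**Conclusion.** The point holds for the interval. Followed as written, the plan yields one percentage as its primary result and a table for accuracy, with no measure of precision for either. For an observed 100% success, the unstated lower limit would be about 83% to 93% if the study has 20 to 50 subjects. That range rests wholly on assumed numbers, but the gap itself does not depend on them.

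The consequence is how firmly feasibility, safety and accuracy are stated. No data are lost and the design is unaffected. I rate it a cheap improvement, at the low end of what should be changed. The denominator is a minor clarification and adds no weight to this rating.

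**What to change.** Amend the SAP's Statistical analysis section as follows.

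1. **Primary outcome:** report n/N, percentage and a two-sided 95% exact (Clopper-Pearson) confidence interval. Wilson would also be acceptable; name one in advance.
2. **Accuracy:** from the fourfold table, report per-subject sensitivity and specificity against EGD for the presence of esophageal disease, as n/N with the same interval. For individual diagnoses with very few EGD-positive subjects, give counts only, since an interval there says almost nothing (1/1 gives 2.5% to 100%).
3. **Adverse events:** report the number and proportion of subjects with any adverse event with the same interval, including when none occurs.
4. **Interpretation:** state conclusions on feasibility and safety alongside these intervals.

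As a separate minor clarification, state that the primary denominator is all enrolled subjects in whom DS-MCE is attempted, and that a failed swallow counts as a failure.

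The accuracy outcome also covers "grade of reflux esophagitis and esophageal varices in comparison to EGD". Agreement on grade does not fit one fourfold table, and this change does not address it.

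The cost is a few sentences and trivial analysis time, with no change to conduct or data collection. The results will look less certain, and counting failed swallows can lower the success rate. The interval shows the imprecision but does not reduce it; only more subjects would.
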